- Patients who request a copy of the consent and HIPAA authorization form prior to the consent visit will be sent copies of these documents via email, delivery (US Postal Service, FedEx, etc.), fax, or text, based upon patient preference. The address or number will be stored in the project database, REDCap.
- Prior to the consent visit, the study staff will review the UCLA electronic health record for study exclusion criteria and if the patient is ineligible, the patient will be contacted, and the in-person visit will be cancelled to avoid unnecessary in-person contact. We will not cancel consent visits for patients who indicate to our staff that the information obtained from the electronic health record is inaccurate.

Step 3 (in-person baseline assessment to determine remaining eligibility criteria: The purpose of the in-person visit will be to further explain the study, obtain written informed consent and begin the baseline assessment. After participants have provided written informed consent (in-person Visit 1), they will complete a baseline assessment that consists of 2 visits (each 45-60 minutes) to the study site.

- Questionnaires included in the baseline assessment:
 - Self-Administered Comorbidity Questionnaire, plus additional questions
 - Insomnia Severity Index (ISI)
 - Pittsburgh Sleep Quality Index (PSQI)
 - Dysfunctional Beliefs and Attitudes about Sleep – 16 item (DBAS-16)
 - Morningness Eveningness Questionnaire (MEQ)
 - Disturbing Dream/Nightmare Severity Index (DDNSI)
 - Restless Leg Syndrome questionnaire (RLS)
 - STOP-Bang questionnaire
 - Epworth Sleepiness Scale (ESS)
 - Brief Pain Inventory (BPI)
 - WHO Quality of Life -BREF (WHOQOL-BREF)
 - Mini-International Neuropsychiatric Interview (MINI) only for participants who have a history of bipolar disorder.
 - Primary Care Post Traumatic Stress Disorder (PC-PTSD)
 - Generalized Anxiety Disorder (GAD-7)
 - Patient Health Questionnaire-Depression Module (PHQ-9)
 - World Health Organization Alcohol, Smoking, and Substance Involvement Screening Test (WHO-ASSIST)
 - Trails A & B tests
 - Digit Symbol Substitution and Symbol Copy
 - Mini-Mental State Examination (MMSE)
 - One-leg standing balance
 - Benzodiazepine Dependence Questionnaire (BDEP)
 - Clinical Institute Withdrawal Assessment Scale – Benzodiazepines (CIWA-B)
 - Credibility/expectancy questionnaire (CEQ)
 - Demographic questions
 - Fall event question

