During week 7 and at the beginning of week 9 of the intervention, participants will only receive the withdrawal symptom assessment. The actual content and structure of the behavioral therapy and tapering protocol will differ between the two groups, although the dose reduction schedule will be the same for the two groups (described below). Intervention sessions will take place in designated, private research rooms/offices at UCLA or at off-campus sites (VA West Los Angeles and Sepulveda campuses). All interventionist sessions (unless participant declined audio-recording during the informed consent process) will be audio-recorded and a random subset will be rated using a structured rating sheet to ensure fidelity to the treatment protocol. The interventionist will also maintain a session-by-session list of information covered and recommendations made. "Progress notes" will be maintained by the interventionist and reviewed during weekly "intervention meetings." These processes will ensure fidelity over the course of the study and avoid the risk of contamination across study arms.

Measures collected during intervention:

A urine sample will be collected from participants at the first intervention session. The urine sample will be tested by a licensed, accredited clinical laboratory (e.g., UCLA clinical lab) for benzodiazepines and zolpidem to confirm the participant's use/nonuse of these hypnotics.

The following measures will be collected weekly throughout the intervention for participants in both study groups.

Clinical Institute Withdrawal Assessment Scale - Benzodiazepines (CIWA-B): This 22-item instrument includes patient symptoms and clinical observations (e.g., tremor) to assess and monitor the type and severity of symptoms of benzodiazepine withdrawal.

Vital signs: These physical examination measurements will be taken weekly: blood pressure, pulse, and respiratory rate.

Insomnia Severity Index (ISI): The ISI is a 7-item instrument that measures perceived severity of insomnia symptoms (total score ranges from 0 to 28).

Epworth Sleepiness Scale (ESS): This 8-item questionnaire assesses general level of daytime sleepiness.

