Daily sleep and habits diary: Participants will use the diary to record bedtime, wake time, total sleep time, time to fall asleep, time awake at night, number of awakenings, napping, exercise, caffeine/alcohol/tobacco use. Participants in the MTcap group only will also record their perceived hypnotic dose taken and their daytime function and sleep quality.

MTcap (Masked Taper plus cognitive behavioral therapy-augmented program):

- a. **Hypnotic taper protocol:** Participants will receive encapsulated hypnotics in a blister taper pack prepared by a compounding pharmacy. Participants will be informed that gradual dose reduction will occur during the program, but they will be blinded to the actual dose they receive each day. The planned rate of reduction of hypnotic will be about 25% per week. The final taper pack will consist of 4 placebo capsules (nights 1-4) and 3 empty blisters (nights 5-7). This planned rate of taper would yield a taper length similar to those reported in other studies, where the average length of taper was 49 days (range 6.5 to 84 days).
- b. **Cognitive behavioral therapy for insomnia-augmented program:** The 8 sessions will incorporate the key components of CBTI (sleep restriction, stimulus control, cognitive restructuring, targeted sleep hygiene) and CBT targeting hypnotic withdrawal. Using the masked doses as a CBT tool, we will add exercises and concepts designed to address and alter expectations for hypnotics. A daily sleep/perceived hypnotic dose diary will be used as a tool for challenging expectancies about hypnotics, refining treatment recommendations, and adjusting the weekly plan. At the last session, the interventionist will inform MTcap participants of the actual doses that they were taking over the 9-week intervention. Participants will be given the taper schedule that the SGT+CBTI group followed unless there was a plateau in the tapering, in which case participants will be shown a revised taper schedule. The interventionist will tell participants the dose that they are currently taking and will review the last week's sleep diary to compare what participants thought they were taking with the actual dose. A study physician will also be available if the participant has specific medical or pharmacological questions about the taper.

SGT+CBTI:

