Participants in the MTcap group will be told the benzodiazepine/z-drug dose that they are taking when they complete the intervention (or if they withdraw before the 9-week intervention period). The primary care providers of participants in both groups will be informed of the final medication regimen, so patients can continue to be monitored for withdrawal, if necessary.

Follow-up assessments

We will encourage participants to complete assessments even if they elect not to complete the intervention. All follow-up assessments will be conducted by research staff who are blinded to group assignment.

Post-treatment assessment

The post-treatment assessment will begin on the same day that the participant completes session 8 of either intervention. At the end of session 8, a participant will be provided with an actigraph to wear at home for 1 week and a sleep and medication diary to complete. When the participant returns the actigraph and diary after 1 week, he/she will be administered selected questionnaires included in the baseline assessment. In addition, a urine sample will be collected to confirm participants' self-report of hypnotic discontinuation. The CURES database will also be queried to obtain data about prescriptions for controlled medications. Participants will also be given a six-month fall log to record any falls they experience during the period between the post-assessment and the six-month follow-up assessment.

Six-month follow-up

The six-month assessment will occur six-months after session 8 is completed (or was scheduled to be completed if a participant drops out of the intervention). This assessment will include 2 visits to the study site. The measures collected will be identical to the post-treatment assessment. At visit 1, the participant will receive an actigraph to wear at home for 1 week, a sleep and medication diary to complete, and selected questionnaires will be administered. At visit 2, the participant will return the actigraph, diary, six-month fall log and will complete additional questionnaires and provide a urine sample. The CURES database will also be queried to obtain data about prescriptions for controlled medications.

Incentives for study participation

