
Confusion about duplicate hypnotic prescriptions: Participants may not understand that the hypnotic provided by the study (in blister packs or medication bottle) replaces the hypnotic that they were previously taking. This could result in participants taking both prescriptions at the same time, which would result in a higher dose than prescribed, and possible side-effects (e.g., daytime sleepiness, dizziness). To avoid confusion about duplicate hypnotic prescriptions, participants in both groups will be asked to bring all their medications to the first intervention session. The interventionist will identify the hypnotic that will be tapered and will place the bottle in a zip-locked plastic bag with a secure plastic tie. A label will be affixed to the outside of the plastic bag that states, "Do not take this medication during the 9-week SWITCH study unless instructed by the study staff." The interventionist

will explain that the participant will receive the same hypnotic either in a new medication bottle or in the blister packs and should put the old prescription in the plastic bag in a safe location.

Increased daytime sleepiness: Adjustments to the participant's sleep habits may result in some initial daytime sleepiness. Daytime sleepiness will be monitored during each weekly in-person intervention assessment with the Epworth Sleepiness Scale, and participants with increased daytime sleepiness will be counseled on the possibility of impaired cognition and increased fall and motor vehicle crash risk. If excessive daytime sleepiness is thought to be due to study-related sleep restriction (as opposed to, for example, a newly-prescribed medication from the individual's physician), the prescribed sleep schedule will be adjusted.

Mental discomfort: The minor risks associated with completion of the questionnaires include tediousness, fatigue, and/or mental discomfort answering the items. Participants could also find wearing the actigraph and WatchPAT device to be annoying or uncomfortable. To reduce the risk of mental discomfort among participants, research staff will be trained to recognize discomfort in participants, and they will be trained to remind participants of the voluntary nature of the research and the option for participants to decline participation in any portion of the research project.

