A chain of custody will be established and documented. Only authorized members of the research team will be permitted to have contact with the medications. A delegation log will be maintained. For both groups, a member of the research team will pick-up the medication bottle or blister packs from the UCLA Research Pharmacy. The medications will be distributed according to the method described above (either pick-up or mailed versus social distancing preferences).

Care coordination at end of intervention period

No change

Follow-up assessments

The post and 6-month assessments will be conducted via video visits for SIP and NIP participants. Procedures similar to the approved in-person protocol will be followed with the following exceptions that will allow for social distancing:

Post-treatment assessment

Preparatory Emails

- (Auto-generated email): A reminder appointment email will be created and invitation for video Post 2 appointment will be sent to the patient
- (Research staff-generated email)
 - Participants will be emailed a confirmation of their Post 2 visit appointment
 - Participants will be provided instructions for preparing for the Post 2 assessment (e.g., anticipated duration, equipment/materials needed, staff contact information)

Getting Materials/Equipment to Participants

- 1) Version for SIP Participants will be advised to pick up Post assessment visit 1 materials (in sealed envelopes) 1 day prior to session 8 and to go to the lab to give urine sample (urine tox and urine zolpidem)
 - Diary
 - Questionnaire packet/instructions
 - Medication log
 - Fall log
 - Wrist actigraph
 - Return Box
- 2) Version for NIP Participants will be mailed Post materials a few days before session 8
 - Diary
 - Questionnaire packet/instructions
 - Medication log
 - Fall log
 - Wrist actigraph
 - Urine specimen container
 - Postage-paid return, insured Return Box

As with the original AIP protocol, the post-treatment assessment will begin on the same day that the participant completes session 8 of either intervention. At the end of session 8, a participant will be instructed to put on the actigraph to wear at home for 1 week and to complete the sleep and medication diary. When the participant returns the actigraph and diary after 1 week, he/she will be administered selected questionnaires included in the baseline assessment. Participants will also be instructed on the six-month fall log to record any falls they experience during the period between the

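### The fall log starts only at the post-treatment assessment, so the 9-week intervention (up to 16 weeks if the taper is extended) has no systematic prospective fall record

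*Combined protocol and SAP*

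**What the plan says.** Under Follow-up assessments, Post-treatment assessment, participants are given "a six-month fall log to record any falls they experience during the period between the post-assessment and the six-month follow-up assessment". The addendum's Post-treatment assessment section repeats this: "Participants will also be instructed on the six-month fall log to record any falls they experience during the period between the" post-treatment and six-month assessments. Participants on the two remote options receive the sheet slightly earlier, in a packet collected one day before session 8 or mailed a few days before it. The period to be recorded is the same.

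The only other fall item is the "Fall event question" in the baseline questionnaire list, with no wording or recall period. At post-treatment "he/she will be administered selected questionnaires included in the baseline assessment", but the selection is not given.

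Under Measures collected during intervention, the lead-in is "The following measures will be collected weekly throughout the intervention for participants in both study groups". The list that follows is the CIWA-B, vital signs, ISI, ESS and a daily diary. The session table under Interventions also schedules side-effect monitoring at every session, with monitoring-only contacts in week 7 and at the start of week 9. Interventionists keep progress notes that are reviewed at weekly meetings.

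Under Potential risks/discomforts, the protocol says "Adjustments to the participant's sleep habits may result in some initial daytime sleepiness" and that "participants with increased daytime sleepiness will be counseled on the possibility of impaired cognition and increased fall and motor vehicle crash risk". Dizziness is listed there as a possible withdrawal symptom. Under Potential direct benefits, falls are among the hypnotic-related health risks that participation may reduce.

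**The concern.** The protocol places a fall hazard inside the intervention and then starts its only fall log once the intervention is over. Participants are over 55, are reducing a hypnotic and are changing their sleep schedule. The sleepiness that prompts the fall counselling is tracked weekly in just this period.

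Two things are at stake. The first is treatment-period safety data: without a set question, whether a fall is recorded depends on the participant raising it and the interventionist writing it down. The second is description by arm: falls during treatment could not be tabulated for MTcap and SGT+CBTI on the same footing as falls during follow-up, although fewer falls is a named potential benefit.

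**Working it through.** The plan states no figure on this point, so there is nothing to reproduce. The check has two parts.

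**1. Does anything listed record falls between session 1 and session 8?**

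- Fall log: no. Its window opens at the post-treatment assessment in both the main protocol and the addendum.
- Daily diary: "Participants will use the diary to record bedtime, wake time, total sleep time, time to fall asleep", then time awake, awakenings, napping, exercise, and caffeine, alcohol and tobacco. MTcap adds perceived dose, daytime function and sleep quality. There is no falls field.
- CIWA-B: described as a 22-item withdrawal scale. Its items are not reproduced, so its content cannot be fully checked.
- Vital signs, ISI and ESS: none is described as covering falls.
- Side-effect monitoring and progress notes: these could capture a fall, but no fall item, definition or form is named.
- Baseline fall question: if repeated at post-treatment it would be retrospective, and the unstated recall period may or may not span the taper.
- Measures in the addendum's video-visit section: the same set, with self-reported blood pressure and pulse.

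**2. How much time is unlogged?**

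Inputs from the documents: the intervention lasts about 9 weeks (Interventions); the taper may be extended to at most 16 weeks (Modified taper plans); the six-month assessment is timed from session 8 (Six-month follow-up).

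Assumptions: six months is 26 weeks; session 8 moves out with an extended taper; logging starts either at session 8 or one week later, at the return visit. The in-person text does not fix the day. It says only that the post-treatment assessment begins on the day of session 8 and runs to the return of the actigraph and diary a week later.

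Unlogged share = (intervention weeks + delay) / (intervention weeks + 26)

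| Intervention | Logging starts at session 8 | Logging starts one week later |
|---|---|---|
| 9 weeks | 9/35 = 26% | 10/35 = 29% |
| 16 weeks (maximum) | 16/42 = 38% | 17/42 = 40% |

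The share of the intervention itself that the log covers is zero in every case. The documents give no fall rate, so the number of unrecorded falls cannot be estimated.

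**The case against.** The best case for the plan is that the intervention is closely supervised and that the precursors of falls are monitored with action attached. ESS is collected weekly, increased sleepiness leads to counselling, and the sleep schedule is adjusted if study-related sleep restriction is thought to be the cause. CIWA-B and vital signs are checked weekly with a defined escalation. Side-effect monitoring takes place at every session, and progress notes are reviewed weekly. The protocol ties its fall warning to sleepiness, not to the taper, for which it lists dizziness. The post-treatment window is also a reasonable place to look for any benefit of stopping the hypnotic. All of this stands. It makes the gap one of systematic recording, not of supervision.

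Four stronger readings are tempting, and the documents do not support them.

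- A reader might infer that a fall during the taper would not reach the study physician. The documents do not say so. Weekly contact and reviewed notes offer a route, and the side-effect forms are not reproduced.
- A reader might infer that logging only the later period makes falls look falsely favourable. That needs falls to be more frequent during treatment, and no fall rate is given. No fall summary is planned, and both arms share the same log window and planned dose-reduction schedule, so the window does not by itself favour an arm.
- A reader might infer that nothing at all could be said about falls during treatment. The baseline question may be repeated, and if its recall period spans the taper some retrospective data by arm would exist.
- A reader might take 40% as typical. It applies only at the maximum extension, and the protocol describes withdrawal symptoms that warrant protocol changes as uncommon.

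What the objection does not supply is a prospective fall record, collected in the same way in both arms, during treatment.

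**Conclusion.** The gap is real and limited in scope. The stated window of the fall log leaves the whole intervention without systematic prospective recording of falls. On the 9-week schedule this is about 26% to 29% of the time from session 1 to six months after session 8, rising to 38% to 40% at the 16-week maximum. The ranges rest on a 26-week six months and on whether logging starts at session 8 or a week later.

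No result that the trial is powered for changes. H1 to H3 do not concern falls, and the exploratory plan covers cognition and balance but not falls. The loss is in treatment-period safety data and in the ability to describe falls by arm in the period to which the protocol's own fall warning applies. The change is worth making because it is cheap and uses materials and contacts that already exist.

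**What to change.** - Give the existing fall log at session 1. For participants on the two remote options, include it in the packet they already receive before session 1. Continue the same log to the six-month assessment.
- Add one falls question to the weekly side-effect check, including the week 7 and early week 9 contacts, and record the answer in the progress notes already reviewed each week.
- State whether the baseline fall question is repeated at post-treatment and six months, and its recall period.
- Report falls by arm, separately for the treatment and follow-up periods, as a descriptive summary.

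The cost is one sheet issued about nine to ten weeks earlier (longer if the taper is extended) and one question per weekly contact. The downside is slightly more recording for participants. Nothing in the taper, the sessions, the escalation pathway or the planned hypothesis tests needs to change.
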